5.0 TREATMENT PLAN

5.1 Treatment Dosage and Administration

Protocol treatment must start within 14 business days of enrollment to the study.

- 5.1.1 In this study, Cohort A and Cohort B patients will start treatment with nivolumab dosed at 3 mg/kg IV and ipilimumab 1 mg/kg every 3 weeks for up to 4 doses. Cohort C patients will receive immunotherapy with nivolumab dosed at a flat dose of 480 mg IV every 4 weeks for up to 26 doses or 104 weeks.
- 5.1.2. Cohorts A and B maintenance immunotherapy with nivolumab dosed at a flat dose of 480 mg IV every 4 weeks will be continued for up to 23 doses or 92 weeks. Missed doses of 480 mg Nivolumab due to toxicity or general health condition will be skipped.

5.1.3 Total protocol therapy for all Cohorts will be up to 104 weeks during treatment. If disease progression or recurrence occurs during the follow-up phase, then per treating physician discretion, the patient may resume nivolumab 480 mg IV every 4 weeks until progression if tolerated with axial imaging as per protocol every, 12 weeks.

5.1.4 All study therapy will be administered on an outpatient basis.

Agent	Precautions	Dose	Route	Schedule	Cycle Length
Nivolumab (solution for injection) induction Cohort A and B only	Administer before other immunotherapy agents	3 mg/kg up to 4 doses	IV infusion over 30 minutes, +/- 10 minutes, with a sterile, nonpyrogenic, low protein binding 0.2 to 1.2 micrometer in-line filter. Follow with saline flush.	Day 1	3 weeks
Ipilimumab (solution for injection) induction Cohort A and B only	Administer 30 minutes after nivolumab.	1 mg/kg up to 4 doses	IV infusion over 90 minutes, +/- 10 minutes, through a non-pyrogenic, low protein-binding in-line filter. Separate IV line required.	Day 1	3 weeks
Nivolumab (solution for injection) maintenance After induction in Cohorts A and B; and throughout in Cohort C	Administer before other immunotherapy agents	480 mg up to 23 doses (92 weeks in Cohort A and B, and 104 weeks in Cohort C)	IV infusion over 30 minutes, +/- 10 minutes, with a sterile, nonpyrogenic, low protein binding 0.2 to 1.2 micrometer in-line filter. Follow with saline flush.	Day 1	4 weeks

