5.4 Duration of Therapy

In the absence of treatment delays due to adverse events, treatment may continue for a total of 104 weeks in all from the start of study therapy or until one of the following criteria apply:

- Disease progression as defined in Section 7.0
- Inter-current illness that prevents further administration of treatment
- Unacceptable adverse event(s)
- Patient voluntarily withdraws from treatment
- General or specific changes in the patient's condition render the patient unacceptable for further treatment in the judgment of the investigator

Do not hold scans, continue scan schedule every 12 weeks from cycle 5 day 1 regardless of treatment delays thereafter.

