6.0 STUDY PROCEDURES

6.1 SCHEDULE OF ASSESSMENTS:

	Screening (within 28 days)	C1D1	C2D1	C3D1	C4D1	D1C5+	EOT¹²	Follow Up⁸
Informed Consent	X							
Review Eligibility Criteria	X							
Demographics, Height	X							
Prior and Concomitant Medications	X	X	X	X	X	X	X	
Review Adverse Events¹⁰	X	X	X	X	X	X	X	
Physical Examination, Vital Signs¹, Weight	X	X	X	X	X	X	X	
ECOG Performance Status	X	X	X	X	X	X	X	
Survival Status								X Q3m
Laboratory Assessments								
Pregnancy Test for WOBCP²	X							
CBC with diff, platelets³	X	X	X	X	X	X	X	
Comprehensive Metabolic Panel, including Alk Phos⁴	X	X	X	X	X	X	X	

	Screening (within 28 days)	C1D1	C2D1	C3D1	C4D1	D1C5+	EOT ¹²	Follow Up ⁸
LDH	X	X	X	X	X			
PSA¹¹	X	X	X	X	X	X	X	X
Testosterone¹¹	X				X		X	
TSH, free T3, free T4 (If Clinically Indicated: FSH, LH, ACTH)	X	X	X	X	X	X ⁶	X	
Therapy								
Cohorts A and B Nivolumab 3 mg/kg IV q3 wks for up to 4 doses¹³				X				
Cohorts A and B Ipilimumab 1 mg/kg IV q3 wks for up to 4 doses¹³				X				
Cohorts A and B Nivolumab 480 mg IV q4 wks for up to 23 doses¹³						X		
Cohort C Nivolumab 480 mg IV q4 wks¹⁴				X		X		
Imaging Tumor Assessments								
CT chest	X					X (q 12 wks)		
CT Abdomen/Pelvis or MRI Abdomen/Pelvis⁵	X					X (q 12 wks)		
Tc^{99m} Bone Scan (prostate only)	X					X (q 12 wks)		
QoL: BPI-SF and EORTC QLQ C30	X					X (q 12 wks)		
Correlatives								
Tumor Tissue Archival (CRPC preferred if available)	X							
Tumor Biopsy	X						X ⁷	
Research blood⁹		X	X	X		X (q 12 wks)	X	

1. Vital signs will include temperature, pulse, respirations, blood pressure; height will be obtained at screening only.
2. WOCBP: Women of child bearing potential; urine or serum pregnancy test.
3. CBC with diff includes total WBC, hemoglobin, hematocrit and differential of the WBC including absolute counts.
4. COMP or Comprehensive metabolic profile includes sodium, potassium, chloride, bicarbonate, BUN, creatinine, AST, ALT, alkaline phosphatase, total bilirubin.
5. With or without intravenous contrast, before or on associated visit. CT or MRI (preferred) brain with or without IV contrast if suspected or known brain metastases. Frequency of tumor assessments will be q12 weeks.
6. Every 42 calendar days ± 14 business days. May be delayed if infusion is not scheduled within the window.
7. Optional tissue biopsy collection at progression if subject consents; +/- 14 working days.
8. Follow up with phone call or with clinic visit.

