9. Blood for research should be collected prior to study treatment on C1D1, C2D1, C3D1 and C5D1, every 12 weeks thereafter and end of treatment.

10. Data on adverse events will be collected from the time of the initial study drug administration through 100 days after the last dose of study drug (nivolumab and/or ipilimumab) as described in Section 8.2.
11. For Cohort A only
12. End of Treatment Visit should occur within 3-4 weeks of last dose of protocol therapy.
13. Cohorts A and B (Nivolumab and Ipilimumab: 1 cycle (C) = 21 days (D) for up to 4 doses of Nivolumab (3mg/kg IV) and Ipilimumab (1mg/kg IV), then Nivolumab maintenance therapy alone (480mg IV): 1 cycle=4 weeks or 28 days (D). Total treatment time is up to 104 weeks.
14. Cohort C (Nivolumab monotherapy): 1 cycle (C) = 28 days (D) of Nivolumab monotherapy (480mg IV) for up to 104 weeks.

NOTE:

All procedures in study assessments schedule have a window of \pm 3 business days unless otherwise mentioned. Virtual clinic visits will be allowed per clinician/ subject discretion.

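### The Section 5.1 dosing table gives Cohort C a cap of 23 nivolumab doses; Section 5.1.1 and the 104-week duration both give 26

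*Combined protocol and SAP*

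**What the plan says.** The table in Section 5.1 has one row for the 480 mg flat dose. Its label assigns it to all three cohorts: "After induction in Cohorts A and B; and throughout in Cohort C". Its dose cell gives one count followed by two durations: "480 mg up to 23 doses (92 weeks in Cohort A and B, and 104 weeks in Cohort C". The cycle length in the row is 4 weeks.

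The numbered text above the table keeps the cohorts apart. Section 5.1.1 gives Cohort C "480 mg IV every 4 weeks for up to 26 doses or 104 weeks". Section 5.1.2 covers maintenance in Cohorts A and B: "480 mg IV every 4 weeks will be continued for up to 23 doses or 92 weeks".

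Other places agree with that text:

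- The schedule of assessments (Section 6.1) ties the count of 23 to two cohorts by name: "Cohorts A and B Nivolumab 480 mg IV q4 wks for up to 23 doses". Its Cohort C row has no dose count, but footnote 14 describes "1 cycle (C) = 28 days (D) of Nivolumab monotherapy (480mg IV) for up to 104 weeks".
- Section 5.4 applies one limit to everyone: "treatment may continue for a total of 104 weeks in all from the start of study therapy".
- The synopsis and Section 5.1.3 also keep Cohort C at 104 weeks.

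**The concern.** For Cohort C the row cannot satisfy both of its own limits. A patient dosed every 4 weeks reaches the 23-dose limit 12 weeks before the 104-week limit. The row also disagrees with Section 5.1.1 on the same page. The number 26 appears nowhere in the row or in the schedule of assessments, so Section 5.1.1 is the only place that states it.

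This is operative dosing text in a multi-site trial, and a dosing table is a natural source for treatment orders. If a site used the count, several protocol clocks would start early for that patient: the end-of-treatment visit (3 to 4 weeks after the last dose, footnote 12 of Section 6.1), adverse event collection (100 days after the last dose, Section 8.2) and the 24-month follow-up (Section 5.6). Duration of therapy, a secondary endpoint, would be shortened. The rule for handling progression could change too. Section 5.4 ends therapy for progression on treatment, while Section 5.1.3 lets a patient who progresses in follow-up resume nivolumab. A patient progressing in the disputed weeks could fall under either rule, depending on which text the site had followed.

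**Working it through.** **Inputs**

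- Cycle length for 480 mg nivolumab: 4 weeks, or 28 days (Section 5.1 table; Section 6.1, footnote 14).
- Table cap: 23 doses, with 92 weeks for Cohorts A and B and 104 weeks for Cohort C (Section 5.1 table).
- Cohort C cap in the text: 26 doses or 104 weeks (Section 5.1.1).
- Induction in Cohorts A and B: up to 4 doses, 3 weeks apart (Section 5.1.1).
- Adverse event collection: to 100 days after the last dose (Section 8.2).

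**Step 1: the plan's figure where it is right.** For Cohorts A and B, maintenance doses = 92 / 4 = 23. Total therapy = 4 × 3 + 23 × 4 = 12 + 92 = 104 weeks. The count of 23 reproduces and agrees with Section 5.1.2.

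**Step 2: the same row for Cohort C.** Cohort C has no induction, so all 104 weeks are on the 4-week schedule. Doses = 104 / 4 = 26. Conversely, 23 × 4 = 92 weeks, not 104. The count of 23 does not reproduce; 26 does.

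**Step 3: size of the gap.**

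- Doses: 26 − 23 = 3, which is 3 / 26 = 11.5% of the maximum.
- Time: 3 × 4 = 12 weeks.
- Drug: 3 × 480 = 1,440 mg.

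**Step 4: calendar consequence with no missed doses.** Taking the first dose as day 1, dose *n* falls on day 28(*n* − 1) + 1.

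| | Table (23 doses) | Section 5.1.1 (26 doses) |
|---|---|---|
| Day of last dose | 28 × 22 + 1 = 617 | 28 × 25 + 1 = 701 |
| Weeks after first dose | 88 | 100 |
| Adverse event window closes | 617 + 100 = day 717 | 701 + 100 = day 801 |

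The difference is 84 days, or 12 weeks, in each case.

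**Step 5: whether skipped doses reconcile the figures.** Section 5.1.2 says "Missed doses of 480 mg Nivolumab due to toxicity or general health condition will be skipped". That sentence sits in the paragraph on Cohorts A and B; suppose it applies to Cohort C as well. With *m* doses missed out of 26 slots, the patient can receive 26 − *m* within 104 weeks, so the table's cap costs max(0, 3 − *m*) doses: 3, 2, 1 and 0 for *m* = 0, 1, 2 and 3. Skipping narrows the gap for some patients but does not remove the contradiction, because 23 and 26 are both maxima.

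**Step 6: effect on the analyses.** Section 11.3 reports the median, if reached, and the 52-week event-free proportion for duration of therapy. Dose 23 falls at week 88, after week 52, so the 52-week figure is unchanged. Nothing in the sample size or the decision rule of 6 responses out of 25 uses the dose count.

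**The case against.** The strongest reply is that 23 was meant for Cohorts A and B only, and that Cohort C was later added to the row by duration alone. On that reading the cell omits a Cohort C count and does not tell anyone to stop at 23. A site would have to ignore the 104 weeks in the same cell, Section 5.1.1 just above it and footnote 14 of the schedule. The patient would also have to be on treatment past week 88 with fewer than three skipped doses.

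Much of this stands. It is probably how the error arose, the correct value can be recovered, and the harm is conditional. The shifted visit, adverse event window and follow-up start are all consequences of one hypothetical early stop. The median duration of therapy could move only if about half of Cohort C were still on treatment around week 88, which nothing in the documents shows.

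It does not make the cell correct. The single count stands before a parenthesis that names all three cohorts, in a row labelled as covering Cohort C throughout. The wording does not limit 23 to Cohorts A and B. Text extraction does not explain it either: the cell reads as one complete phrase, and a lost line break would not remove a 26.

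**Conclusion.** The concern holds. For Cohort C the table's 23 doses contradict the 26 doses of Section 5.1.1 and the row's own 104 weeks. The intended figure is not in doubt, and the error is confined to this cell.

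The most it can cost is 3 doses (1,440 mg, 12 weeks) per affected patient. That maximum assumes dosing every 4 weeks with none missed; the smaller losses after missed doses assume that the skip rule in Section 5.1.2 also governs Cohort C. Only patients who would receive a 24th dose are exposed, and their number cannot be worked out from the documents. No effect on the primary PSA analysis, sample size or power is shown. The cell should be corrected because it is a dosing instruction.

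**What to change.** Reword the dose cell so that each count sits with its cohort: 480 mg, up to 23 doses (92 weeks) in Cohorts A and B; up to 26 doses (104 weeks) in Cohort C. Both figures are already in Sections 5.1.1 and 5.1.2. Adding the 26-dose count to the Cohort C row of the schedule of assessments would help but is optional.

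The cost is one table cell in the next amendment, with no effect on design or analysis.

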5.2 Toxities and Dosing Delays/Dose Modifications

Any patient who receives treatment on this protocol will be evaluable for toxicity. Each patient will be assessed for the development of toxicity according to the Time and Events Table (Section 6.1). Toxicity will be assessed according to the NCI Common Terminology Criteria for Adverse Events (CTCAE), version 4.03. Dose changes of either study drug is NOT permitted. Doses can be held however as necessary. Dosing holds should be made according to the system showing the greatest degree of toxicity.

Adverse Event Related vs Unrelated Dose Delays: If dose delay is due to an unrelated Adverse Event then reason for hold must be documented. Any patient on this protocol will be allowed to continue to receive study treatment at the investigator's discretion, regardless of AE relatedness. Do not have to delay dose for unrelated Adverse Event.

5.2.1 Treatment delay for toxicity of more than 84 days from last intended therapy will result in treatment discontinuation for the specific drug(s) responsible for the toxicity. If ipilimumab is permanently discontinued, then discontinue Nivolumab 3mg/kg. Nivolumab 480 mg can be continued.

5.2.2 Investigators should consider dose re-calculation of ipilimumab with change in weight as per standard of care/institutional guidelines. However, a change in weight by 10% or more should lead to a dose re-calculation.

5.2.3 Nivolumab and/or ipilimumab cannot be dose reduced in response to toxicity, and can only be held or discontinued as per detailed algorithms for immune-therapy toxicity management below.

NCI CTCAE v 4 Grade	Nivolumab	Ipilimumab
0-1	No change from original starting dose	No change from original starting dose
2	Withhold drug, resume treatment when adverse reaction improves to grade 0 or 1	Withhold drug, resume treatment when adverse reaction improves to grade 0 or 1
3	Withhold drug, resume treatment when adverse reaction improves to grade 0 or 1 when given as a single agent	Withhold drug, resume treatment when adverse reaction improves to grade 0 or 1
Second episode of grade 3 or any episode of grade 4 toxicity	Permanently discontinue therapy and remove subject from trial	Permanently discontinue therapy and remove subject from trial

Certain adverse events that are possibly immune mediated warrant special monitoring and management, and are outlined below to guide investigators.

5.2.4.1 Pulmonary:

Rule out non-inflammatory causes. If non-inflammatory cause, treat accordingly and continue protocol therapy. Evaluate with imaging and pulmonary consultation.

Grade of pneumonitis (NCI CTCAE v4)	Management	Follow-up
Grade 1 Radiographic changes only	
Consider delay nivolumab or ipilimumabMonitor for symptoms every 2-3 daysConsider pulmonary and infectious disease consultations	
Re-image at least every 3 weeks 
If worsens:
 
If worsens:
 
Treat as Grade 2 or 3-4

Grade 2 Mild to moderate new symptoms	
 Delay nivolumab or ipilimumab Consult pulmonary and infectious disease Monitor symptoms daily, consider hospitalization 1.0-2.0 mg/kg/day methylprednisolone IV or oral equivalent Consider bronchoscopy and/or lung biopsy 	
 Re-image every 1-3 days 
If improves: If improves:
 
 When symptoms return to near baseline, taper steroids over at least one month and resume nivolumab and ipilimumab per protocol and consider prophylactic antibiotics 
If not improving after 2 weeks or worsening:
 
 Treat as Grade 3-4 
If not improving after 2 weeks or worsening, treat as grade 3 or 4

Grade 3 or 4 Severe new symptoms; New/worsening hypoxia; Life-threatening	
 Discontinue nivolumab or ipilimumab Hospitalize Consult pulmonary and infectious disease 2-4 mg/kg/day methylprednisolone IV or IV equivalent Add prophylactic antibiotics for opportunistic infections Consider bronchoscopy and/or lung biopsy 	
If improves to baseline:
 
 Taper steroids over 6 weeks 
If not improving after 48 hours or worsening:
 
 Add additional immunosuppression

5.2.4.2 Gastrointestinal:

Rule out non-inflammatory causes. If non-inflammatory is identified, treat accordingly and continue protocol therapy. Opiates/narcotics may mask symptoms of perforation. Infliximab should not be used in case of perforation or sepsis.

Grade of diarrhea/colitis (NCI CTCAE v4)	Management	Follow-up
Grade 1 Diarrhea: < 4 stools/day over baseline; Colitis: asymptomatic	
 Continue nivolumab or ipilimumab per protocol Symptomatic treatment 	
 Close monitoring for worsening symptoms Educate patient to report worsening immediately 
If worsens:
 
 Treat as Grade 2 or 3/4
Grade 2 Diarrhea: 4-6 stools per day over baseline; IV fluids indicated <24 hrs; not interfering with ADL	
 Delay nivolumab and ipilimumab per protocol Symptomatic treatment 	
If improves to grade 1: Resume nivolumab or ipilimumab per protocol
 
If persists > 5-7 days or recur:

Grade of diarrhea/colitis (NCI CTCAE v4)	Management	Follow-up
Colitis: abdominal pain; blood in stool		
 0.5-1.0mg/kg/day methylprednisolone or oral equivalent When symptoms improve to grade 1, taper steroids over at least 1 month, consider prophylactic antibiotics for opportunistic infections, and resume nivolumab or ipilimumab per protocol 
If worsens or persists > 3-5 day with oral steroids:
 
 Treat grade 3/4
Grade 3-4 Diarrhea (G3): ≥7 stools per day over baseline; incontinence; IV fluids ≥24 hrs; interfering with ADL Colitis (G3): severe abdominal pain, medical intervention indicated, peritoneal signs G4: life-threatening, perforation	
 Discontinue nivolumab or ipilimumab per protocol 1.0 to 2.0 mg/kg/day methylprednisolone IV or IV equivalent Add prophylactic antibiotics for opportunistic infections Consider lower endoscopy 	
If improves:
 
 Continue steroids until grade 1, then taper over at least 1 month 
If persists > 3-5 days, or recurs after improvement:
 
 Add infliximab 5 mg/kg (if no contraindication). 
Note: Infliximab should not be used in cases of perforation or sepsis

5.2.4.3 Endocrinopathy:

Rule out non-inflammatory causes. If non-inflammatory cause, treat accordingly and continue protocol therapy. Consider visual field testing, endocrinology consultation and imaging.

Endocrinopathy	Management	Follow-up
Asymptomatic thyroid-stimulating hormone (TSH) elevation	
 Continue nivolumab or ipilimumab If TSH $<0.5 \times$ LLN, or TSH $>2 \times$ ULN, or consistently out of range in 2 subsequent measurements: include free T4 at subsequent cycles as clinically indicated; consider endocrinology consult 	
Symptomatic endocrinopathy	
 Evaluate endocrine function Consider pituitary scan 
Symptomatic with abnormal lab/pituitary scan:
 
 Delay study therapy per protocol 1-2 mg/kg/day methylprednisolone IV or PO equivalent Initiate appropriate hormone therapy 
No abnormal lab/pituitary MRI scan but symptoms persist:
 
 Repeat labs in 1-3 weeks / MRI in 1 month 	
If improves (with or without hormone replacement):
 
 Taper steroids over at least 1 month and consider prophylactic antibiotics for opportunistic infections Resume protocol therapy per protocol Patients with adrenal insufficiency may need to continue steroids with mineralocorticoid component
Suspicion of adrenal crisis (e.g. severe dehydration, hypotension, shock out of proportion to current illness)	
 Delay or discontinue nivolumab or ipilimumab per protocol Rule out sepsis Stress dose of IV steroids with mineralocorticoid activity IV fluids Consult endocrinologist If adrenal crisis ruled out, then treat as above for symptomatic endocrinopathy 	

5.2.4.4 Hepatic:

Rule out non-inflammatory causes. If non-inflammatory cause, treat accordingly and continue protocol therapy. Consider imaging for obstruction.

Grade of Liver Test Elevation (NCI CTCAE v4)	Management	Follow-up
Grade 1 AST or ALT > ULN to 3 x ULN and/or total bilirubin > ULN to 1.5 x ULN	
 Continue nivolumab or ipilimumab 	
 Continue liver function test (LFT) per protocol 
If worsening:
 
 Treat as Grade 2 or 3-4
Grade 2 AST or ALT > 3.0 to \leq 5 x ULN and/or total bilirubin > ULN to 1.5-to \leq 3 x ULN	
 Delay nivolumab or ipilimumab per protocol Increase frequency of monitoring to every 3 days 	
If returns to baseline:
 
 Resume routine monitoring, resume nivolumab or ipilimumab 
If persists > 5-7 days or worsens:
 
 0.5-1 mg/kg/day methylprednisolone or oral equivalent and when LFT returns to grade 1 or baseline, taper steroids over at least 1 month, consider prophylactic antibiotics for opportunistic infections, and resume nivolumab and ipilimumab
Grade 3 or 4 AST or ALT > 5 x ULN and/or total bilirubin > 3 x ULN	
 Discontinue nivolumab or ipilimumab* Increase frequency of monitoring to every 1-2 days 1.0 to 2.0 mg/kg/day methylprednisolone IV or IV equivalent* Add prophylactic antibiotics for opportunistic infection Consult gastroenterologist 	
If returns to grade 2:
 
 Taper steroids over at least one month 
If does not improve in > 3-5 days, worsens or rebounds:
 
 Add mycophenolate mofetil 1g twice daily If no response within an additional 3-5 days, consider other immunosuppressive agents per local guidelines

*The recommended starting dose for grade 4 hepatitis is 2 mg/kg/day methylprednisolone IV.

5.2.4.5 Neurological:

Rule out non-inflammatory causes. If non-inflammatory cause, treat accordingly and continue protocol therapy.

Grade of neurological toxicity (NCI CTCAE v 4)	Management	Follow-up
Grade 1 Asymptomatic or mild symptoms; intervention not indicated	
 Continue nivolumab or ipilimumab 	
 Continue to monitor the patient. 
If worsens:
 
 Treat as grade 2 or 3-4
Grade 2 Moderate symptoms; Limiting instrumental ADL	
 Delay nivolumab or ipilimumab Treat symptoms per institutional guidelines Consider 0.5-1mg/kg per day methylprednisolone IV or oral equivalent 	
If returns to baseline:
 
 Resume nivolumab or ipilimumab 
If worsens:
 
 Treat as Grade 3 - 4
Grade 3 or 4 Severe symptoms; Limiting self-care ADL; Life-threatening	
 Discontinue nivolumab or ipilimumab Consult Neurology Treat symptoms per institutional guidelines 1-2mg/kg per day IV methylprednisolone or IV equivalent Add prophylactic antibiotics for opportunistic infections 	
If improves to grade 2:
 
 Taper steroids over at least one month 
If worsens or atypical presentation:
 
 Consider IVIG or other immunosuppressive therapies per institutional guidelines

5.2.4.6 Skin:

Rule out non-inflammatory causes. If non-inflammatory cause, treat accordingly and continue protocol therapy

Grade of Rash (NCI CTCAE v4)	Management	Follow-up
Grade 1-2 Covering ≤ 30% body surface area (BSA)*	
 Symptomatic therapy (e.g. antihistamines, topical steroids) Continue nivolumab or ipilimumab 	
If persists > 1-2 weeks or recurs:
 
 Consider skin biopsy Delay nivolumab or ipilimumab Consider 0.5-1mg/kg/day methylprednisolone IV or oral equivalent. Once improving, taper steroids over at least 1 month, consider prophylactic antibiotics for opportunistic infections, and resume nivolumab or ipilimumab 
If worsens:
 
 Treat as Grade 3-4

Grade 3-4 Covering >30% BSA; or life threatening consequences*^	
 Delay or discontinue nivolumab or ipilimumab Consider skin biopsy Consult dermatology 1-2mg/kg/day methylprednisolone IV or IV equivalent 	If improves to grade 1: 
 Taper steroids over at least one month and add prophylactic antibiotics for opportunistic infections Resume nivolumab or ipilimumab
---	--	---

*Refer to NCI CTCAE v4 for term-specific grading criteria.

[^]If SJS/TEN is suspected, withhold I-O therapy and refer patient for specialized care for assessment and treatment. If SJS or TEN is diagnosed, permanently discontinue nivolumab and ipilimumab

5.2.4.7 Renal:

Rule out non-inflammatory causes. If non-inflammatory cause, treat accordingly and continue protocol therapy

Grade of elevation in serum creatinine (NCI CTCAE v4)	Management	Follow-up
Grade 1 Serum creatinine > ULN and > than baseline but \leq 1.5 x baseline	
 Continue nivolumab /or ipilimumab Monitor serum creatinine weekly 	If returns to baseline: 
 Resume creatinine monitoring per protocol If worsens: 
 Treat as Grade 2, 3/4
Grade 2-3 Serum creatinine > 1.5 x baseline to \leq 6 x ULN	
 Delay nivolumab or ipilimumab Monitor serum creatinine every 2-3 days 0.5 to 1.0 mg/kg/day methylprednisolone IV or oral equivalent Consider renal biopsy with nephrology consult 	If returns to Grade 1: Taper steroids over at least 1 month, consider prophylactic antibiotics for opportunistic infections, and resume nivolumab and ipilimumab and routine serum creatine monitoring per protocol If elevations persists > 7days or worsen: 
 Treat as Grade 4
Grade 4 Serum creatinine > 6 x ULN	
 Discontinue nivolumab or ipilimumab Monitor serum creatinine daily 1-2mg/kg/day methylprednisolone IV or IV equivalent Consult nephrology Consult renal biopsy 	If returns to Grade 1: 
 Taper steroids over at least one month and add prophylactic antibiotics for opportunistic infections

5.2.4.8 Myocarditis:

Rule out non-inflammatory causes. If non-inflammatory cause, treat accordingly and continue protocol therapy

Grade of Rash Myocarditis (NCI CTCAE v4)	Management	Follow-up
Grade 2 Symptoms with mild to moderate activity or exertion	
 Delay nivolumab or ipilimumab hospitalization with cardiac monitoring Urgent cardiology consultation for evaluation and management 
 Troponin and BNP ECG ± continuous cardiac monitoring Echocardiogram Cardiac MRI Prompt initiation of 2 mg/kg/day methylprednisolone IV or equivalent 	
 If worsens, intensify treatment according to grade Upon recovery, taper steroids over at least 1 month with close monitoring of troponin and BNP as well as for new symptoms Repeat cardiac MRI for post treatment assessment and cardiology follow-up Retreatment may be considered after recovery and completion of steroid taper
Grade 3: Severe with symptoms at rest or with minimal activity or exertion; intervention indicated Grade 4: Life threatening consequences; urgent intervention indicated (e.g., continuous IV therapy or mechanical hemodynamic support)	
 Permanently discontinue nivolumab or ipilimumab Hospitalize to intensive cardiac monitoring 
 Cardiac evaluation to include: Troponin and BNP monitoring ECG ± continuous cardiac monitoring Echocardiogram Cardiac MRI Myocardial biopsy if feasible Immediate initiation of 2 mg/kg/day methylprednisolone IV or 1 g IV bolus Consider adding a second immunosuppressive agent 
Additionally, for Grade 4:
 
 Hospitalize/transfer to institution with expertise in intensive cardiac monitoring Consider ATG as second agent given its immediate effect 	
 If no improvement, consider additional immunosuppression Upon recovery, taper steroids over at least 1 month with close monitoring of troponin and BNP as well as for new symptoms Repeat cardiac MRI for post treatment assessments and cardiology follow-up

5.2.4.9 Ocular manifestations:

Monitor patients for signs or symptoms of ocular toxicity, which may include blurred vision and reduced visual acuity. Immune-mediated ocular toxicity may be associated with retinal detachment or permanent vision loss. Administer corticosteroid eye drops to patients who develop uveitis, iritis, or episcleritis. Permanently discontinue ipilimumab for immune-mediated ocular disease that is unresponsive to local immunosuppressive therapy. If uveitis occurs in combination with other immune-mediated adverse reactions, consider a Vogt-Koyanagi-Harada-like syndrome, which has been observed in patients receiving ipilimumab and may require treatment with systemic steroids to reduce the risk of permanent vision loss.

5.2.4.10 Other:

For rare cases of myotoxicity (myositis, myocarditis, and rhabdomyolysis), some with fatal outcome, have been reported with nivolumab or nivolumab in combination with ipilimumab. If a patient develops signs and symptoms of myotoxicity, close monitoring should be implemented, and the patient referred to a specialist for assessment and treatment without delay. Based on severity of myotoxicity, nivolumab or nivolumab in combination with ipilimumab should be withheld or discontinued, and appropriate treatment instituted.

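### The investigator-discretion sentence in Section 5.2 also covers drug-related AEs of any grade, so as worded it contradicts the protocol's own hold and stop rules, and no text says which governs

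*Combined protocol and SAP*

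**What the plan says.** A run-in paragraph in Section 5.2, headed as dealing with related and unrelated dose delays, makes three statements in order. A hold for an unrelated AE must have its reason documented. Then: "Any patient on this protocol will be allowed to continue to receive study treatment at the investigator's discretion, regardless of AE relatedness". Last, an unrelated AE need not delay a dose.

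The specific rules follow:

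- **5.2.1:** a toxicity delay of more than 84 days ends treatment with the drug or drugs responsible.
- **5.2.3 table, grade 2:** both drugs are withheld until recovery to grade 0 or 1.
- **5.2.3 table, grade 3:** ipilimumab is withheld in the same way. The nivolumab cell carries a qualifier: "Withhold drug, resume treatment when adverse reaction improves to grade 0 or 1 when given as a single agent".
- **5.2.3 table, second grade 3 or any grade 4:** "Permanently discontinue therapy and remove subject from trial".
- **5.2.4.6, SJS/TEN footnote:** "If SJS or TEN is diagnosed, permanently discontinue nivolumab and ipilimumab".
- **5.2.4.8, myocarditis grade 3 or 4:** "Permanently discontinue nivolumab or ipilimumab".
- **5.2.4.9, ocular:** "Permanently discontinue ipilimumab for immune-mediated ocular disease that is unresponsive to local immunosuppressive therapy".

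Section 5.4 lists unacceptable adverse events among the reasons to end treatment, and 5.5 requires removal when a 5.4 criterion is met. Neither defines the term or ties it to 5.2.

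**The concern.** The discretion sentence sets aside relatedness in express terms and names no grade, event type or exception. The rules below it do depend on grade and event, and some end treatment for good. The organ sections also let cause decide whether dosing goes on: "If non-inflammatory cause, treat accordingly and continue protocol therapy". A site could cite the discretion sentence to keep dosing after a drug-related event at which another site would stop permanently, and it would be arguable whether that was a protocol deviation.

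The hazards are serious. Section 9.2 acknowledges that immune-mediated reactions to ipilimumab can be fatal, and 5.2.4.10 reports deaths from myotoxicity with nivolumab alone or in combination. The protocol limits discretion in other places: continuing after a prohibited medication needs the agreement of three parties (5.3), and treatment beyond progression has four listed conditions (7.2). The AE sentence has no such limit.

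**Working it through.** The plan states no figure on this point, so the check is textual.

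**Step 1: three readings of the discretion sentence against each rule.**

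| Rule | A. Unrelated AEs only | B. A delay alone does not end participation | C. Literal: any AE, any grade |
|---|---|---|---|
| 5.2.1, delay over 84 days | Compatible | Partly conflicts: a long delay does end the responsible drug | Conflicts |
| 5.2.3, withhold rows | Compatible | Compatible | Conflicts |
| 5.2.3, last row | Compatible | Conflicts | Conflicts |
| 5.2.4.6, SJS/TEN | Compatible | Conflicts | Conflicts |
| 5.2.4.8, myocarditis grade 3-4 | Compatible | Conflicts | Conflicts |
| 5.2.4.9, ocular (ipilimumab) | Compatible | Conflicts | Conflicts |

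Column A assumes that toxicity and adverse reaction in these rules mean drug-related events. Only A removes every conflict, and A does not match the words: the next sentence already covers unrelated AEs, so on that reading the phrase about relatedness would do nothing. Section 5.3 uses nearly the same phrase for patients given palliative radiation, where it plainly permits dosing.

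**Step 2: is there a rule of precedence?** Four places come close.

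- The rule in 5.2 about the system with the worst toxicity only selects which organ system drives a hold.
- The lead-in to the 5.2.3 table bars dose reduction and confines holds and stops to the algorithms that follow. It is the nearest thing to a ranking, but it does not mention the discretion sentence.
- The lead-in to 5.2.4 presents the event-specific text as guidance, which points the other way.
- Sections 5.4 and 5.5 make removal mandatory, but on an undefined criterion.

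No sentence ranks the texts.

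**Step 3: size.** Directives worded as permanent: 1 (5.2.3 last row) + 3 (5.2.4.6, 5.2.4.8, 5.2.4.9) = 4. They overlap, because grade 4 myocarditis is already in the 5.2.3 last row. Planned patients under the sentence: 25 + 15 + 25 = 65. Planned for ipilimumab, to whom the ocular directive can apply: 25 + 15 = 40 (Cohorts A and B). These are planned enrolments, not counts of affected patients.

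**The case against.** The strongest defence is context. The paragraph concerns dose delays, and the statements on either side are about unrelated AEs. The 5.2.3 lead-in comes later, is more specific and is mandatory in tone. On the ordinary principle that the specific governs the general, discretion would operate only where no rule directs a hold or stop. An event that the table says must end treatment also fits naturally under unacceptable adverse events in 5.4. Reporting of SAEs to the principal investigator and Coordinating Center within 24 hours, quarterly DSMC review and monitoring for adherence further limit the risk.

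Most of this stands as evidence of intent. It makes it likely that the authors meant reading A, and a reader who inferred that the protocol sets out to permit dosing through severe related toxicity would go beyond the documents. It does not change what the sentence says, and the oversight steps do not tell a site which rule applies.

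Two further inferences are tempting. One is that every stop instruction in 5.2.4 is a binding command that the sentence breaks. The documents do not support that: the section is introduced as guidance, the pulmonary grade 3-4 row says "Discontinue nivolumab or ipilimumab" without the word permanently, and the diarrhea/colitis row refers back to the protocol. The guidance lead-in also covers the three permanent directives, which weakens them somewhat. The conflict with 5.2.1 and with the 5.2.3 table, both outside that lead-in, remains even if 5.2.4 is set aside.

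The other is that the stricter of 5.2.3 and 5.2.4 should always prevail. Whether the organ rows really are stricter at a first grade 3 event is unsettled, and the choice is a separate clinical decision.

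**Conclusion.** The point holds as a defect of wording with a safety consequence. The sentence probably means that unrelated AEs need not delay dosing. As written it reaches related AEs of any grade and contradicts 5.2.1, the 5.2.3 table and the three permanent-stop directives in 5.2.4, with no text to resolve the conflict. The conflict is firmest at the 5.2.3 last row, which ends treatment outright and is not introduced as guidance.

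The conclusion rests on the literal wording and the absence of a precedence statement. It does not assume that any site has used the sentence to override a stop rule; the documents show no such case. The decision rules in 11.1 are unaffected. Only the descriptive proportions of patients with AE-related removals and dose holds in 11.3 could shift, by an amount that cannot be derived.

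**What to change.** Make two changes to the dose-delay paragraph of 5.2:

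1. Limit the discretion to continue to AEs judged unlikely or unrelated on the attribution scale in 8.4.2.
2. Add that for AEs judged possibly, probably or definitely related, the hold and discontinuation rules in 5.2.1 and 5.2.3 and the permanent-discontinuation directives in 5.2.4.6, 5.2.4.8 and 5.2.4.9 apply and are not subject to investigator discretion.

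This keeps the likely intent. It also makes clear that the three named directives stop treatment where the 5.2.3 table alone might only call for a hold, such as a first grade 3 myocarditis. Other differences between 5.2.3 and 5.2.4 are left to the clinical team.

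The cost is a protocol amendment of about two sentences and a notice to sites. It needs no new procedures, visits or patients, and no change to the sample size or analysis.
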